## **8.4 Recruitment and consent procedure**

Members of the TVTs at participating trusts will identify eligible patients. A record of those identified as eligible, approached to participate, refusals, consenting patients and questionnaire returns will be made (see section 7.4.1 and 7.5). The recruitment and consent methods described above in the preliminary field test will be used (section 7.4).

In addition to the information described in section 7.4, the patient information leaflet for the final field test indicates that participants can take part in 2 ways: 1) self-complete or administered questionnaire booklet at baseline, and if they agree, 2) complete a second self-complete or administered questionnaire booklet 2-7 days later. There will be an option on the consent form where participants can indicate whether they agree to take part in a second questionnaire. In addition to the original consent form being filed within the PURPOSE Investigator Site File or designated secure location, one copy for the patient, and one for the patient's medical notes, a copy of the consent form will be sent to the CTRU.

### **Self-complete version**

If patients who self-complete a questionnaire at baseline agree, they will provide home address details so that a second questionnaire booklet can be given to them when the first booklet is collected or sent out to them with a return stamped, self-addressed envelope. Where patients are still hospital in-patients, they will complete the second questionnaire on the ward and return it to the researcher or TVT member that provided it to them.

### **Interview-administered version**

If patients who were administered a questionnaire at baseline agree, they will provide home address details so that a second questionnaire booklet can be administered to them at a time agreed by the patient and the person administering the questionnaire (must be between 2-7 days after baseline administration). Where patients are still hospital in-patients, they will have a second questionnaire pack administered to them on the ward. The researcher or TVT member that administered the questionnaire pack will be responsible for returning completed questionnaires to CTRU.

## **8.5 Data collection/assessments**

Study data will be recorded by members of the TVTs on the CRFs and by patients on questionnaire packs. Data will be returned to the CTRU.

Assessments will be undertaken as follows:

- Registration and Baseline
- PU-QOL Questionnaire booklet

- 2-7 day follow-up questionnaire pack (approx. 75 patients from baseline sample)

### **8.5.1 Registration and baseline Data**

Baseline information will be recorded by the TVT member including:

- Patient initials and date of birth
- Gender
- Ethnicity
- Marital status
- Education
- Presence of PU symptoms
- Pressure ulcer grade, location and number of pressure ulcers
- Duration of pressure ulcer
- Treatment plan (information about which treatment interventions the patient is currently receiving)
- Co-morbidity and/or speciality (i.e. spinal cord injured, trauma, vascular, care of the elderly ward)
- Centre code
- Name of the TVT/clinical research staff member conducting registration
- Confirmation of eligibility and written informed consent
- Braden scale

### **8.5.2 PU-QOL questionnaire pack**

Baseline questionnaire pack will include:

- The Provisional PU-QOL
- SF-12 (rather than SF36 to reduce respondent burden)
- Additional questionnaires selected for validation purposes (ethics will be notified about which questionnaires are selected, section 8.5.3)

Test-retest questionnaire pack will include:

- The Provisional PU-QOL
- SF-12 (rather than SF36 to reduce respondent burden)
- Additional questionnaires selected for validation purposes (ethics will be notified about which questionnaires are selected, section 8.5.3)

### **8.5.3 Assessment instruments**

#### **The Short Form-12 Health Survey Questionnaire**

Use of the SF-36 was considered however it was decided by the project team that it was too long for use with PU patients. Instead, the SF-12 will be used to reduce respondent burden. The SF-12 is a generic instrument that assesses HRQL in eight domains of physical functioning, role-physical, body pain, general health, energy/fatigue, social functioning, role-emotional and mental health. These are the same domains as the SF-36. Even though this instrument has not been validated for use with PU patients, it has been used with other related chronic-skin wound conditions to validate their corresponding disease-specific HRQL instruments.

#### **Additional questionnaires**

Participants will complete the short version of the PU-QOL, the SF-12, and additional measures to assess construct validity (convergent, discriminant, known groups). The guiding principle in selecting the validating measures will be to include measures that will allow a comparison of PU-QOL subscales with measures of similar constructs (convergent validity) and with measures of different constructs (discriminant validity), and to compare PU-QOL scores in clinically defined known groups whose HRQL would be expected to differ. At this stage it is not possible to anticipate the subscales and item stem of the PU-QOL until it has been developed (pre-testing, section 6). As such, selection of validating measures is not possible. However, where available, short versions of measures selected for validation purposes and only measures deemed essential for validation testing will be included in the questionnaire packs. All measures will be administered in the same order. It is anticipated that completion of questionnaire packs may take up to an hour.

### **8.6 Psychometric evaluation analysis**

Analyses will include examination of:

**Item-level performance** will determine missing data (<5%), maximum endorsement frequencies (<80%), and item redundancy (inter-item correlations <0.75).

**Acceptability** will be assessed by completeness of data (e.g. missing data for summary scores <5%) and score distributions (e.g. distribution of endorsement frequencies across response categories, skew and floor/ceiling effects for summary scores <10%).

**Reliability** will be assessed on the basis of internal consistency (Cronbach's alpha for summary scores  $\geq 0.70$  and item-total correlations  $\geq 0.30$ ) and test-retest reliability (correlations for summary scores  $\geq 0.70$ ).

**Validity** will include a within-scale analyses to determine whether a single entity (construct) is being measured and that items on the measure can be combined to form a summary score (Cronbach's alpha  $\geq 0.70$ ), and analysis against external criteria (convergent, discriminant and known groups differences validity). To evaluate convergent validity we will compare PU-QOL with the SF-12, and additional relevant measures as determined once the PU-QOL questionnaire is developed. Discriminant validity will be assessed by examining PU-QOL scores by age, gender and medical specialty. PU-QOL scores for patients by PU severity (superficial vs severe), site of PU (heel vs elsewhere), and sensitivity impaired vs. no sensitivity impaired will be compared to evaluate known group differences. Factor analysis, together with the results of other item-level analyses described in table 2, will be used to investigate hypothesised subscales.

**Evaluation of subscales** will be determined by factor analysis and item convergent/discriminant validity

In addition to standard psychometric tests, modern psychometric methods will be used to strengthen methodological rigour [36].

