### **Test-Retest**

A test-retest will be undertaken with a sub-sample of participants recruited for the final field test. Consenting participants will complete a second questionnaire pack 2-7 days after the first questionnaire pack (approximately 75 patients for each mode of administration group). The length of the test-retest interval must be short enough to ensure that clinical change in the PU is unlikely to occur, but sufficiently long to ensure that respondents do not recall their responses from the first assessment. A short test-retest interval is necessary to ensure that stability per se is being evaluated, rather than clinical change in the PU during the test-retest interval, which will underestimate reliability.

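### Test-retest reliability is judged by an unqualified correlation of at least 0.70, which on its own cannot show that scores are stable between administrations

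*Protocol*

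**What the plan says.** Section 8.6 (Psychometric evaluation analysis), under Reliability, gives the whole retest criterion: "test-retest reliability (correlations for summary scores" must reach 0.70. The coefficient is not named. The same section uses the word for ordinary correlations elsewhere, for example "item redundancy (inter-item correlations <0.75" and the item-total correlations. The protocol nowhere mentions an intraclass or concordance coefficient, a mean retest difference or limits of agreement.

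Section 8.3 (Test-Retest) sets out the design and its purpose:
- Timing: "Consenting participants will complete a second questionnaire pack 2-7 days after the first questionnaire pack".
- Size: "approximately 75 patients for each mode of administration group", with no derivation.
- Purpose of the short interval: "A short test-retest interval is necessary to ensure that stability per se is being evaluated, rather than clinical change in the PU".
- Lower limit on the interval: it must be "sufficiently long to ensure that respondents do not recall their responses from the first assessment".

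**The concern.** The retest is there to show that a patient whose ulcer has not changed gets about the same score twice. An ordinary correlation answers a narrower question: do patients keep their relative positions? If every patient scores half a standard deviation lower the second time, the correlation is the same as if nobody had moved. A consistency-type ICC has the same blind spot.

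The protocol's procedures leave room for a common shift, although they do not document one. Section 7.4.1 accepts a possible completion bias when the attending team member collects the questionnaire, and section 8.4 carries the section 7.4 procedures into field test 2. For self-completing patients, section 8.4 allows the second booklet to be posted out and returned by post, so the setting can differ between occasions. Section 8.5.3 expects a pack to take up to an hour.

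At stake is the meaning of a change score. Section 4.1 wants an instrument suitable for clinical trials, and section 5.1 lists responsiveness among the properties to be evaluated. The retest is the only repeat administration that the protocol describes, so it is the only place where drift in stable patients could be seen.

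**Working it through.** The plan has no figure to reproduce: 0.70 is a chosen cut-off, and the 75 retests per mode group have no derivation. The check is therefore how a correlation and an agreement coefficient respond to a common shift.

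**Inputs.** From the protocol: the 0.70 threshold (section 8.6) and n = 75 (section 8.3). Assumed, because the protocol gives neither: the correlation r and the mean shift d in SD units, both shown over a range. Also assumed: equal SDs on the two occasions.

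**Formula.** Take each SD as 1. The between-patient variance is r, the residual variance is 1 − r, and the variance between two occasions that differ by d is d²/2. Hence

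absolute-agreement ICC = r / (1 + d²/2).

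Neither the ordinary correlation nor the consistency ICC contains d.

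**Examples.**
- r = 0.75, d = 0.5: 0.75 / 1.125 = 0.667. The correlation passes and agreement fails.
- r = 0.70, d = 0.3: 0.70 / 1.045 = 0.670.
- r = 0.70, d = 0.5: 0.70 / 1.125 = 0.622.
- r = 0.80, d = 0.3: 0.80 / 1.045 = 0.766. Both pass.
- r = 0.80, d = 0.5: 0.80 / 1.125 = 0.711. Both pass.

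**Shift at which agreement falls to 0.70.** Solving gives d = √[2(r/0.70 − 1)]:

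| r | d (SD) |
|---|---|
| 0.70 | 0 (any shift fails) |
| 0.75 | 0.38 |
| 0.80 | 0.54 |
| 0.90 | 0.76 |

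**Chance of an observed value of at least 0.70** with n = 75 and true r = 0.80 (simulation, normal scores, 20,000 samples):

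| Shift (SD) | Ordinary correlation | Consistency ICC | Absolute-agreement ICC |
|---|---|---|---|
| 0 | 98% | 97% | 98% |
| 0.3 | 98% | 98% | 90% |
| 0.5 | 98% | 97% | 58% |
| 0.8 | 98% | 98% | 3% |

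The first two columns do not respond to the shift. With no shift, the three rules agree.

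**Precision.** For an observed correlation of 0.70 with n = 75, the Fisher-z interval is tanh(0.867 ± 1.96/√72), which is 0.56 to 0.80.

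**The case against.** The strongest reply is that the text does not say Pearson. An intraclass correlation is also a correlation, the list in section 8.6 is introduced as what the analyses will include, and the exact coefficient and its interval are often left to a statistical analysis plan. This stands in part. The type is indeed open, and if an absolute-agreement ICC was meant, the fault is one of wording only. But the protocol itself states both the statistic and the pass mark, and the neighbouring uses of the word are ordinary correlations. The absence of a confidence interval, by contrast, is a reporting detail. It applies equally to the other thresholds in section 8.6 and is not a fault by itself.

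Second, the sentence in section 8.3 justifies the length of the interval; it does not promise a test of absolute agreement. That is true, but it does name stability as what the retest evaluates, and the criterion should be able to show it.

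Third, a reader might infer that scores will drift, or that passing the criterion would be a false result. The documents do not support that. They give no expected shift, the pack has the same listed contents on both occasions (section 8.5.2), and the measures come in the same order (section 8.5.3). Shifts up to about 0.3 SD cost little unless r is close to 0.70. The example of 0.75 against 0.67 is also a smaller gap than the sampling error at n = 75.

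Fourth, in a randomised comparison a shift common to both arms largely cancels, so the harm falls mainly on before-after interpretation. This stands.

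Fifth, absolute agreement also registers real mean change over 2 to 7 days, so a low value need not be the instrument's fault. This stands too, and is why the coefficient has to be read with the mean difference.

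**Conclusion.** The point holds in a limited form. On its plain reading, the only stated retest criterion does not respond to a common shift, so it cannot by itself show the stability that section 8.3 describes. Scores that shift can therefore pass.

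The size depends on values that the protocol does not give. With equal SDs assumed, the conclusion reverses for r near 0.70 with almost any shift, for r = 0.75 with a shift above about 0.38 SD, for r = 0.80 above about 0.54 SD, and for r = 0.90 above about 0.76 SD. With a strong correlation and a small shift, the two criteria give the same answer. It would go too far to say that the criterion is certainly a Pearson correlation, or that unstable scores are likely to pass.

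**What to change.** In section 8.6, replace the unqualified term by the two-way, single-measure, absolute-agreement ICC for each summary score, with the criterion kept at 0.70 or above and its 95% CI reported. Alongside it, report the mean retest difference with its CI for each mode group, so that a low ICC caused by a mean shift can be told apart from poor ranking of patients.

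The cost is a change of wording. The data, the retest interval and the planned 75 or so retests per mode group stay as they are. The downside is that the coefficient will be lower, possibly clearly lower, if there is a shift. Part of any shift may be real change over 2 to 7 days, so the ICC must be interpreted together with the mean difference. If an absolute-agreement ICC was intended all along, the edit only makes that explicit.

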## **12 ETHICAL CONSIDERATIONS**

This project will recruit patients with PUs and therefore will include elderly and highly dependent patients considered as vulnerable. Ethical issues are largely related to the involvement of vulnerable adults/elderly patients with high levels of co-morbidity including acute and chronic illness. Clinically, older patients are treated in the same way as younger patients and it is therefore important to ensure that the study is representative of the clinical population. In addition, questionnaire completion/interview requires the patient to reflect on their experience of having a PU and how interventions received have impacted on their QOL. For some people this may raise topics considered to be sensitive, embarrassing or upsetting, and possibly emotionally distressing.

The ethical issues surrounding these potentially vulnerable patients have been addressed through the study design and include a thought out consent process, the use of one-to-one

semi-structured interviews using de-briefing questioning for data collection at the development pre-testing stage to provide a caring and supportive environment in which to discuss any sensitive issues that may arise, and the use of only essential measures required for validation purposes (short version where available) to reduce respondent burden. If the patient becomes distressed during the interview or from completing the questionnaire, then the interview will be immediately stopped. It will be stressed to all patients that they are able to withdraw from participation at any time without giving reason, and without any effect on their care. They will be referred back to their treating nurse specialist if required.

This study will be conducted in accordance with the Declaration of Helsinki in its latest form. The study will be submitted to and approved by a REC prior to identifying eligible patients. The CTRU will provide the REC with a copy of the final protocol, patient information leaflets, consent forms, and all other relevant study documentation.

## **APPENDIX 1 – MODE OF ADMINISTRATION SUBSTUDY**

## **BACKGROUND TO SUB-STUDY**

Initially, the purpose of the PU-QOL study was to develop and psychometrically evaluate a HRQL questionnaire for patients with pressure ulcers as a self-complete mode of administration questionnaire. However, preliminary analysis of the pre-test data has identified problems with completion rate, posing a question about the appropriateness of a self-complete measure for patients with pressure ulcers, particularly elderly patients aged over 80 years. To address these methodological issues identified from the pre-test, we are proposing to undertake a mode of administration sub-study. The sub-study will determine the mode of administration for which the questionnaire will be developed and validated.

### **Aim and objectives**

The purpose of the sub-study is to determine whether one questionnaire can be developed and validated for use with both modes of administration or whether two mode-specific questionnaires are required.

## **METHODS**

### **Design**

A mode of administration sub-study including a differential item functioning (DIF) analysis [37] will be undertaken to establish measurement equivalence across two mode of administration groups (self-complete and interview-administered modes). A DIF analysis will investigate the equivalence of the PU-QOLs' questionnaire items by comparison of these two groups.

A sample of 60-100 patients are required for the sub-study. Consecutive patients will be approached to take part. Eligible patients who provide written informed consent will be randomised to either the self-complete or interview-administered groups (see section 2.2).

We plan to develop one PU-QOL questionnaire – the results of the sub-study will determine whether PU-QOL should be developed as interview-administered only OR both self-complete and interview-administered (see section 5 for more details).

### **Eligibility**

To ensure an equivalent or representative sample in both mode of administration groups (i.e. both groups need to have the same clinical presentation to perform a differential item

functioning analysis, see section 6), the eligibility criteria has been adapted from the main study to include only patients who are able to read and write in English (i.e. patients able to self-complete a questionnaire will be randomised to both mode of administration groups).

Patients from participating acute and community NHS Trusts, with existing PUs (any grade, see Table 1), will be included in the sub-study if they are hospital in-patients or outpatients, intermediate care patients, nursing home patients or community patients under the care of community care nursing services, and they fulfil the criteria detailed below in section 2.2.1. Patients who took part in pre-testing will not be approached to take part in the sub-study.

### **Inclusion criteria**

- aged  $\geq 18$  years **and**
- with an existing PU of any grade, location, or duration **and**
- able to provide informed consent to participate **and**
- able to read and write in English (i.e. able to self-complete a questionnaire)

### **Exclusion criteria**

Patients will also be excluded from the study if any of the following criteria apply. They:

- have only moisture lesions
- are unconscious or confused
- have cognitive impairment
- are unable to read or write in English
- they do not have an existing PU **or**
- are unable to provide informed consent

Patients who are deemed ethically inappropriate to approach by members of the Tissue Viability Team (TVT), for example, those where death is imminent (any patient who is on or meets the criteria of the Liverpool Care Pathway for the dying) will not be approached.

### **Recruitment and consent**

Members of the TVTs at participating trusts will identify eligible patients for the sub-study. A record of those identified as eligible, approached to participate, refusals, consenting patients and questionnaire returns will be made (see section 3.1).

A verbal explanation of the study and patient information leaflet will be provided by the TVT member or the researcher\* (CG) for the patient to consider. These will include detailed information about the rationale, design and personal implications of the study. Following information provision, patients will have as much time as they need to consider participation and will be given the opportunity to discuss the study with their family and healthcare professionals before they are asked whether they would be willing to take part. The right of the patient to refuse consent without giving reasons will be respected.

Should the patient be capable of giving consent but physically unable to complete the written aspects of the consent form, witnessed consent should be obtained using the Witnessed Consent Form. An appropriate witness would be a family member or friend of the patient or another member of the patient's healthcare team who is not directly involved in the research study.

*\*Where the researcher is involved in the recruitment and consent process, the patient will be asked to give verbal permission to be approached by the researcher*

Assenting patients will then be invited to provide informed, written consent to collect baseline assessment data and to complete the questionnaire. Formal eligibility assessment and informed consent will be undertaken by the TVT member or researcher. The patient will remain free to withdraw from the study at any time without giving reasons and without prejudicing any further treatment. The original consent form will be filed within the PURPOSE Investigator Site File or designated secure location. One copy of the consent form will be given to the patient and one will be filed with the patients medical file.

### **Screening and registration**

The TVT member will complete a log of all patients screened for eligibility who are not randomised or registered either because they are ineligible or because they declined participation. All screening logs will be returned to the CTRU.

Anonymised information will be collected including:

- The reason not eligible for study participation **or**
- Eligible but declined
- Date of Birth
- Gender

- Ethnicity
- Pressure ulcer grade and location

